15.8. Response Review

Not applicable.

15.9. Unblinding Procedures

Not applicable.

Version Date: 11/09/2017

15.10. Stopping Rules

The study may be discontinued if the study is terminated by the data and safety monitoring committee, the Food and Drug Administration (FDA), or other regulatory authorities.

Any unforeseen deaths or serious adverse events may, after a discussion between the principal investigator and investigators at other sites, prompt an interruption to study accrual pending a full investigation into the circumstances surrounding the event.

15.11. Other Response Parameters

Not applicable.

16. DATA REPORTING / REGULATORY REQUIREMENTS

Adverse event lists, guidelines, and instructions for AE reporting can be found in Section 10 (Adverse Events: List and Reporting Requirements). The Data Safety Monitoring Plan is described in Section 16.

16.1. Data Collection

The Herbert Irving Comprehensive Cancer Center has an electronic clinical trials and data management system (CTMS) that will be used for data collection. Case report forms (CRFs) for the study will be built into the CTMS for data entry. The system has full auditing capabilities which is web-based and housed on a server in a fully HIPAA compliant server room with restricted access and video camera monitoring. All users must login with their own application username and password. Users off campus must first access the Virtual Private Network with their assigned campus username and password and then use their application credentials. Users are only able to see study information if they are indicated as study personnel in our electronic IRB system. Users are limited to access based on the role assigned in their corresponding protocol. Subject data is entered directly into the system, which (in the case of Columbia subjects) confirms the correct identity of patients via an interface with the electronic medical patient index. Staff with the appropriate IRB defined roles can run reports within the system for reporting purposes.

16.2. Data Reporting

Case Report Forms will be completed for each subject enrolled into the clinical study through the CTMS. It is the investigator's responsibility for ensuring that all clinical and laboratory data entered on the corresponding CRFs are complete, accurate and authentic.

Version Date: 11/09/2017

16.3. Data and Safety Monitoring Committee

The NCI-approved Data Safety and Monitoring Committee (DSMC) of the Herbert Irving Comprehensive Cancer Center (HICCC) will monitor every subject who receives treatment on this protocol for toxicity. This protocol will adhere to the policies of the currently approved HICCC Data and Safety Monitoring Plan (DSMP), which is in accordance with NCI and CUMC-IRB policy and guidelines. The committee chair is appointed by the HICCC Director. The committee consists of HICCC faculty and staff with expertise in oncology, research pharmacy, research nursing, and data management. The DSMC convenes twice a month to review patient safety and the conduct of the trial. The PI will submit data and safety monitoring reports to the DSMC at a frequency to be determined by the DSMC based on risk to the subjects.

At the time of renewal, the study team will submit the most recent DSMC approval letter for safety review to the CUMC IRB. Any modifications that are required by the DSMC to ensure patient safety will be submitted to the IRB. All protocol deviations, violations, and eligibility waivers will be submitted to and approved by the DSMC prior to being reported to the IRB. All study data reviewed and discussed during these meetings will be kept confidential.

For multicenter research, the principal investigator will assure that there is a mechanism in place to distribute the report to all participating investigators for submission to their local IRB. The report will document that a review of data and outcomes across all centers took place on a given date. It will summarize the DSMC's review of the cumulative toxicities reported from all participating sites without specific disclosure by treatment arm. It will also inform site investigators of the study the DSMC's conclusion with respect to progress or need for modification of the protocol.

16.4. Quality Control and Quality Assurance

Independent monitoring of the clinical study for protocol and GCP compliance will be conducted periodically by the CPDM Compliance Core on behalf of the HICCC DSMC. Additionally, the Compliance Oversight Committee of the IRB at Columbia University Medical Center may audit the study at any time per institutional policies and procedures. The investigator-sponsor and Columbia University Medical Center will permit direct access of the study monitors and appropriate regulatory authorities to the study data and to the corresponding source data and documents to verify the accuracy of this data.

A risk-based approach will be used by the Compliance Core to determine the frequency, number of subject charts, and data elements to be monitored. The Compliance Coordinator will review the study status and summarize enrollment, toxicities, SAEs/UPs, dose escalation, statistical endpoints (e.g., stopping rules), etc. for the full DSMC membership at the regularly scheduled meetings.

Internal On-site Monitoring:

Version Date: 11/09/2017

- Initial, recurrent, and close-out on-site monitoring visits will also be conducted at remote clinical sites, as appropriate/feasible. Other sites will have monitoring performed remotely (see below for further details).
- The study Monitoring Visit Log will be completed and signed by the monitor and the PI/CRNP/CRN and/or CRC and will be filed in the regulatory binder.
- The Compliance Coordinator will communicate with the site coordinator/Site Principle Investigator to schedule the monitoring visit and arrange for access to study materials and documentation.
- The assigned Compliance Coordinator will monitor IIT trials within 1 month after the first subject is enrolled and throughout the life of the study to ensure that the study is being conducted in accordance with the protocol, GCP, applicable federal and local regulations, and per all applicable SOPs. The Compliance Coordinator is responsible to notify the PI and CRNP/CRN/CRC of upcoming monitor visits and convey what information and documentation will be required for the visit(s). The Compliance Coordinator is responsible for verifying that informed consent is properly obtained, eligibility is met (via the central registration process), and all study procedures are conducted according to the study protocol. The Compliance Coordinator will also verify that the data reported in the CRF's accurately reflect source documents, that all toxicities have been reported to date, and that all SAE's/UPs/deviations/violations have been reported according to local IRB and HICCC DSMC requirements. The Compliance Coordinator will issue queries and ensure resolution in a timely and efficient manner. The Compliance Coordinator will also monitor for applicable regulatory compliance and research pharmacy compliance (if applicable) and communicate any deficiencies as appropriate.

16.5. Confidentiality

Information about study subjects will be kept confidential and managed according to the requirements of the Health Insurance Portability and Accountability Act (HIPAA). Those regulations require a signed subject authorization informing the subject of the following:

- What protected health information (PHI) will be collected from subjects in this study
- Who will have access to that information and why
- Who will use or disclose that information
- The rights of a research subject to revoke their authorization for use of their PHI.

In the event that a subject revokes authorization to collect or use PHI, the investigator, by regulation, retains the ability to use all information collected prior to the revocation of subject authorization. For subjects that have revoked authorization to collect or use PHI, attempts should be made to obtain permission to collect at least vital status (e.g., that the subject is alive) at the end of their scheduled study period.

The subject binders will be maintained with in the CPDM offices, a secured floor within the Herbert Irving Pavilion and only the investigator and study staff will have access to the file.

Version Date: 11/09/2017

16.6. Source Documents

Source data is all information, original records of clinical findings, observations, or other activities in a clinical trial necessary for the reconstruction and evaluation of the trial. Source data are contained in source documents Examples of these original documents, and data records include: hospital records, clinical and office charts, laboratory notes, memoranda, subjects' diaries or evaluation checklists, pharmacy dispensing records, recorded data from automated instruments, copies or transcriptions certified after verification as being accurate and complete, microfiches, photographic negatives, microfilm or magnetic media, x-rays, subject files, and records kept at the pharmacy, at the laboratories, and at medico-technical departments involved in the clinical trial.

16.7. Case Report Forms

The study case report form (CRF) is the primary data collection instrument for the study. All data requested on the CRF must be recorded. All missing data must be explained. If a space on the CRF is left blank because the procedure was not done or the question was not asked, write "N/D". If the item is not applicable to the individual case, write "N/A".

16.8. Records Retention

Records relating to a specific research activity, including research records collected by investigators, must be maintained for at least three years after completion of the research (45 CFR 46.115(b); 21 CFR 56.115(b); 21 CFR 312.62). This minimum retention period applies whether or not any subjects were enrolled in the study.

If the research is FDA regulated, records should be retained for at least two years after approval of the investigational agent by FDA; if it is not approved, records should be retained at least two years after the study is terminated and FDA is notified (note the additional requirement below for clinical research studies).

Clinical records, including consent forms that document clinical intervention or clinical diagnostic procedure research-related procedures, must be retained in medical records by the institution for at least seven years, per CUMC and NYP policy which is based on state law.

17. STATISTICAL CONSIDERATIONS

17.1. Study Endpoints and Analysis Plan

Definition of primary outcome/endpoint:

The primary endpoint is the overall response rate defined as the best response within the first 24 weeks of the start of study therapy using RECIST v. 1.1 that has been confirmed at a subsequent

time point (\geq 4 weeks).

Definition of secondary outcomes/endpoints:

PFS is defined as time from enrollment to time of clinical or radiographic disease progression as defined by RECIST v.1.1 criteria. OS is defined as time from enrollment to time of death from any cause.

Analytic plan for primary objective:

We will estimate the response rate to combination therapy with epacadostat and pembrolizumab using the exact 95% confidence interval based on the binomial distribution.

Analytic plan for secondary and exploratory objectives:

- We will estimate the survival distribution for both PFS and OS endpoints using the Kaplan Meier method. The log rank test will be used to examine differences between survival curves using prognostic markers such as KIT mutation status.
- For correlative studies we will apply either the Fisher's exact test or Wilcoxon rank sum test to examine the correlation between response status and markers for categorical and continuous variables, respectively. Because of the limited sample size, the biomarker data analysis is for exploratory research only.

Sample Size Justification

The primary endpoint of this trial is the objective response rate defined as the best response within the first 24 weeks of the start of study therapy using RECIST v1.1 criteria, and that has been confirmed at a subsequent time point (≥4 weeks).. We will use a Simon mini-max two-stage design with a target objective response rate of 20%, compared to a historical response rate of 5% with salvage tyrosine kinase inhibitor monotherapy¹⁰, and the probabilities of type I and type II error set at 0.1 and 0.2 respectively. In the first stage, 12 patients will be accrued. If less than 1 patient achieves a response among the initial 12 patients, the study will be declared negative and terminated. If at least 1 patient achieves a response, an additional 9 patients will be accrued to the second stage for a total of 21 evaluable patients. If at least 3 total patients achieve a response, that treatment will be declared positive for attaining the primary endpoint. This study design yields at least 80% power to detect a 20% response rate (compared to the null hypothesis of 5%) at a significance level of 10%. There is a 54% chance of stopping at Stage 1 if the true confirmed response rate is at most 5% (null hypothesis). Accounting for 10% dropout, we will plan to enroll a total of 23 patients.

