5. STUDY DESIGN

5.1 General study design

This is a single-arm Phase 2 study to evaluate the efficacy of combined epacadostat and pembrolizumab in advanced imatinib-refractory GIST patients.

Study Intervention: All subjects will receive pembrolizumab 200 mg IV every 3 weeks and epacadostat 100 mg PO BID continuously.

Schedule of Evaluations: Subjects will have regularly scheduled study visits at the clinical site on Day 1 of every cycle (CXD1), where safety assessments, including laboratory assessments, vital signs, and physical examinations will be performed (see Section 12 for detailed study evaluations, and Section 13 for study calendar).

Response to treatment will be determined by CT scans of the chest, abdomen, and pelvis with contrast. The overall response rate for the primary endpoint evaluation will be determined by RECIST v1.1 criteria; however, clinical decision making may be made based on immune related RECIST (irRECIST) criteria to allow treatment beyond initial progression (see section 15). In patients who are unable to get a CT scan w/ contrast due to renal function (or any other reason), an MRI with and without contrast may be used instead. Imaging will be performed at the following time points:

Baseline scan	Baseline scan within 4 weeks prior to first treatment
Weeks 1 – 24	Every 6 weeks +/- 1 week (at weeks 6, 12, 18, 24)
Weeks 25 – until disease	Every 12 weeks +/- 1 week (at weeks 36, 48, 60, 72, 84, 96, 108)
progression	
2 years	If subjects achieve ongoing disease control at 2 years, patients will be taken off study treatment and observed with imaging every 12 weeks +/- 2 weeks. If the patient develops disease progression, the option of reinitiating study therapy may be considered.

Version Date: 11/09/2017

Duration of treatment: Subjects will continue treatment until confirmed radiographic disease progression, intolerable toxicity or side effects (see Section 6.6 for Criteria for Withdrawal) or ongoing disease control at 2 years. In the latter case, imaging will be performed every 12 weeks, and should the patient develop evidence of disease progression, the option of reinitiating study therapy may be considered based upon discussion with the study principal investigator.

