5.2. Number of subjects

Using a Simon two-stage design, 12 patients will be treated initially. If an objective response is observed in at least 1 patient, we will proceed with enrollment of an additional 9 patients for a total of 21 evaluable patients. Assuming a 10% drop-out rate, we anticipate a total maximal accrual of 23 patients.

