8.7. Treatment After Initial Evidence of Radiographic Disease Progression

Version Date: 11/09/2017

Immunotherapeutic agents such as pembrolizumab and epacadostat may produce antitumor effects by potentiating endogenous cancer-specific immune responses. The response patterns seen with such an approach may extend beyond the typical time course of responses seen with cytotoxic agents and can manifest as a clinical response after an initial increase in tumor burden or even the appearance of new lesions.

If radiologic imaging shows progressive disease (PD), tumor assessment should be repeated ≥ 4 weeks later to confirm PD, with the option of continuing treatment for clinically stable subjects while awaiting radiologic confirmation of progression. Clinically stable may be defined by the following criteria:

- Absence of signs and symptoms indicating disease progression
- No decline in ECOG performance status
- Absence of rapid progression of disease
- Absence of progressive tumor at critical anatomical sites (eg, cord compression) requiring urgent alternative medical intervention

In determining whether the tumor burden has increased or decreased, investigators should consider all target lesions as well as non-target lesions. Subjects who are deemed clinically unstable are not required to have repeat imaging for confirmation. If radiologic progression is confirmed, then the subject will be discontinued from study treatment as specified in the Protocol, and the first radiographic evidence of PD should be the date of progression. If radiologic progression is not confirmed, then the subject should resume/continue study treatment and have their next scan according to the Protocol-specified schedule.

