- 9. See section 12.2.2 for assessment of serotonin syndrome.
- 10. CT chest, abdomen, and pelvis with contrast to assess tumor status will be performed at baseline (within 28 days prior to Cycle 1 Day 1 of treatment) and then every 6 weeks (+/-1 week) during the first 24 weeks of study treatment. Imaging of the area with known disease involvement only (ex: CT chest only or CT abdomen/ pelvis only) is allowed for week 6 and week 18 tumor assessments at the investigator's discretion. After week 24, a CT chest, abdomen, pelvis with contrast will be performed every 12 weeks (+/-1 week). In patients who are unable to get a CT scan with contrast due to renal function (or any other reason), a CT chest without contrast and MRI abdomen/ pelvis with and without contrast may be used instead.
- 11. A fresh tumor biopsy will be performed at baseline within screening period, prior to C1D1 of treatment. Archived FFPE slides are not acceptable. This biopsy is mandatory. However, subjects in whom biopsy is technically not feasible or in whom would result in unacceptable risk, in the opinion of the investigator, may be exempted from the biopsy requirement with discussion with the principal investigator.
- 12. On-treatment biopsy will be obtained anytime between C2D1 and C3D1 (prior to starting cycle 3). This biopsy is mandatory. However, subjects in whom biopsy is technically not feasible or in whom would result in unacceptable risk, in the opinion of the investigator, may be exempted from the biopsy requirement with discussion with the principal investigator.
- 13. Blood for ctDNA will be collected on day $1 \pm 3d$ for cycles 1-3, and then day $1 \pm 3d$ of every other cycle thereafter. In addition, blood for PBMC collection will be collected on cycle 1 day 1 and cycle 2 day 1 (\pm 3d). See section 14.1.2 for collection instructions.
- 14. A fasting blood sample for PD analysis will be collected on Cycle 1, Day 1 (pre-dose) and Cycle 2, Day $1 \pm 3d$ (pre-dose and +2 hours (+/-30 minutes)), and at the end of treatment. See section 14.1.3 for collection instructions.
- 15. One full cycle (21 days) supply of epacadostat will be dispensed at the beginning of each subsequent cycle. Cycle 2, Day 1 epacadostat dose will be administered in clinic (for PD blood sample studies).

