15. MEASUREMENT OF EFFECT

15.1. Antitumor Effect – Solid Tumors

Initial tumor imaging must be performed within 28 days before the first dose of study treatment. For the purposes of this study, patients should be re-evaluated for response every six weeks within the first 24 weeks, then every 12 weeks for the remainder of study duration (Section 7.2.6). The study will utilize RECIST v.1.1, with responses confirmed at ≥4 weeks, for determination of the primary endpoint of ORR. The immune related RECIST (irRECIST), which is adapted for defining PD to account for the unique tumor response seen with immunotherapies (section 15), will be applied for clinical assessment of tumor response and as a basis for treating subjects beyond initial radiographic progression.

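### Does a response first seen at the week-24 scan lack a confirming scan and leave the stage-1 decision undefined?

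*Combined protocol and SAP*

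**What the plan says.** Section 17.1 gives the endpoint twice. Under the primary outcome it reads: "best response within the first 24 weeks of the start of study therapy using RECIST v. 1.1 that has been confirmed at a subsequent" assessment. The sample-size paragraph repeats the 24-week window and adds "and that has been confirmed at a subsequent time point (≥4 weeks"). Neither sets a latest date for confirmation. The same paragraph then gives the Simon rule: stop if none of 12 responds, otherwise add 9 patients, and call the treatment positive with at least 3 responders in 21. It closes with "There is a 54% chance of stopping at Stage 1 if the true confirmed response rate is at most 5" per cent.

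Section 5.2 summarises patient numbers more loosely: "If an objective response is observed in at least 1 patient, we will proceed with enrollment of an additional 9 patients".

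On imaging, section 15.1 says "patients should be re-evaluated for response every six weeks within the first 24 weeks, then every 12 weeks for the remainder of study duration". The schedule in section 5.1 lists weeks 6, 12, 18 and 24, each within a week either way, and then "Every 12 weeks +/- 1 week (at weeks 36, 48, 60, 72, 84, 96, 108"). Table 10, footnote 10, in section 13 agrees: "After week 24, a CT chest, abdomen, pelvis with contrast will be performed every 12 weeks (+/-1 week"). For apparent progression, section 8.7 adds that "tumor assessment should be repeated ≥ 4 weeks later to confirm PD", and section 15.5 repeats this. No matching instruction exists for a response. Section 12.5 allows unscheduled visits when medically warranted, and Table 12 provides a scan at treatment discontinuation.

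**The concern.** The scan interval doubles at week 24, the last scan that can supply a first response. A response seen there faces a longer test of durability than one seen at week 6, 12 or 18, and its status stays open in the meantime. The protocol itself expects some late responses: section 8.7 notes that immunotherapy responses can follow an initial increase in tumor burden.

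The thresholds make one patient matter, because stage 1 turns on a single response in 12. If the only one is first seen at week 24, section 5.2 could be read as allowing accrual to continue at once. Section 17.1 ties the stopping probability to confirmed responses, and no section mentions a data cut-off, an accrual hold or a pending response. Section 15.10, on stopping rules, does not mention the look at all. Stopping on such a patient would abandon a trial whose own rule might say continue. Counting responses that never confirm would loosen error control.

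**Working it through.** **Scan gaps** (sections 5.1 and 13; each scan may move one week either way)

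- Week 6 to 12, 12 to 18, or 18 to 24: 6 − 2 = 4 weeks to 6 + 2 = 8 weeks.
- Week 24 to 36: 12 − 2 = 10 weeks to 12 + 2 = 14 weeks.

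The requirement is at least 4 weeks with no maximum. Every gap meets it, including the last.

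**The plan's own figures** (section 17.1: 12 then 9 patients, stop at 0, positive at 3 or more of 21, rates 5% and 20%)

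- Early stop at 5%: 0.95^12 = 0.5404, the stated 54%.
- Type I error: P(at least 3 of 21) − P(0 of 12) × P(at least 3 of 9) = 0.0849 − 0.5404 × 0.0084 = 0.0804, within the stated 10%.
- Power at 20%: 0.8213 − 0.0687 × 0.2618 = 0.8033, the stated 80%.

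These hold when stage 1 counts confirmed responses and waits for any that are pending.

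**How often one patient decides stage 1**

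- Exactly one responder in 12 at 20%: 12 × 0.20 × 0.80^11 = 0.2062.
- Exactly one responder in 12 at 5%: 12 × 0.05 × 0.95^11 = 0.3413.

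These count a sole responder whenever first seen. The problem needs that responder to be a week-24 first response as well. Let f be the share of confirmed responders first seen at week 24. The documents do not give f, so it is an assumption. For f from 0.10 to 0.30 the joint probability is 0.2062 × f = 2.1% to 6.2% at a true 20%, and 0.3413 × f = 3.4% to 10.2% at 5%. The response must also still be pending at the look. A patient who started 14 or more weeks before the 12th will have reached the week-36 scan by the time the 12th has the week-24 scan (37 − 23 = 14, the worst case of both windows).

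**What the other readings would do** (assumed values)

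1. Week-24 first responses ignored at stage 1 but counted at the end. The chance of stopping at a true 20% is (1 − 0.20(1 − f))^12. Power is the sum over x ≥ 1 of P(x of 12) × (1 − f^x) × P(at least 3 − x of 9).

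| f | Stop at stage 1, true 20% | Power |
|---|---|---|
| 0 | 6.9% | 80.3% |
| 0.10 | 9.2% | 78.9% |
| 0.20 | 12.3% | 76.8% |
| 0.30 | 16.4% | 73.9% |

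2. Unconfirmed responses counted at both stages, with a further 1 to 3 percentage points of patients having a week-24 response that never confirms. Early stopping at a true confirmed rate of 5% becomes 0.94^12 = 47.6% to 0.92^12 = 36.8%, and type I error rises to 12.2% to 22.3%.

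**Which reading the text supports.** The second departs from the endpoint definition, which requires confirmation. The first calls the count zero while a qualifying response is still open. Section 17.1 defines the response as confirmed, then states the stage-1 rule, then gives the stopping probability for the confirmed rate. Fewer than one responder in 12 cannot be established until a pending response is resolved.

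**Cost of waiting.** If the 12th patient has the pending response, the stage-1 result moves from weeks 23–25 to weeks 35–37 after that patient's first dose.

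**The case for a change.** The best case for a change is that the alternatives are not harmless. Under the assumed shares, ignoring pending responses takes power below 80%, and counting unconfirmed ones takes type I error above 10%. A rule chosen once the pending patient is known would be data-driven, section 5.2 leaves out confirmation, and the synopsis can be read as requiring confirmation inside the 24 weeks. Unscheduled scans are allowed but not required, so sites might differ in how soon they confirm.

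Some of this stands. The plan has no explicit sentence on pending responses, sections 5.2 and 17.1 are worded differently, and the longer gap after week 24 is real. But the damaging figures belong to readings that the statistical section does not support. Section 5.2 is a short summary of numbers and is a weak basis for redefining the endpoint. Section 17.1 is clearer than the synopsis and places confirmation at a later time point. The final comparison with 3 of 21 has no unstated rule either, since the week-36 scan can confirm a week-24 response there too. A mandatory repeat scan would shorten the wait but add a procedure for a gain that the documents give no means to size.

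**Conclusion.** The concern does not call for a change. The confirming scan for a week-24 response exists on the schedule at week 36, and an earlier unscheduled scan is not ruled out. The 10-to-14-week interval asks more of a late response, which makes a positive result harder to reach, not easier. That is a fair trade-off for the lighter imaging schedule after week 24.

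The silence on pending responses is a gap that a statistician following section 17.1 fills sensibly: count confirmed responses, and declare no stop while the only candidate among the 12 is unresolved. The stated 80% power and 54% early stopping are then correct. The situation cannot arise with a sole responder more often than 20.6% (true rate 20%) or 34.1% (true rate 5%). It will arise less often, because that patient must also respond first at week 24 and still be pending at the look. When it does, the price is about 12 weeks. This rests on reading the stage-1 rule together with the endpoint in its own paragraph. The size of f is unknown, and no loss of power is claimed. Aligning section 5.2 with 17.1 would be tidy, but no result depends on it.

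### The planned binomial 95% interval ignores the stop at 0/12, so it is not exact for this two-stage design and its upper limit is too low at 1/21 and 2/21

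*Combined protocol and SAP*

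**What the plan says.** Section 17.1, under the analytic plan for the primary objective, reads: "We will estimate the response rate to combination therapy with epacadostat and pembrolizumab using the exact 95% confidence interval based on the binomial distribution". The Statistical Methodology row of the synopsis repeats it. Section 17.3 asks again for 95% confidence intervals without naming a method. No point estimator is named anywhere.

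The sample size justification in 17.1 describes sampling in two stages:

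- Stage 1 enrols 12 patients.
- The futility rule is: "If less than 1 patient achieves a response among the initial 12 patients, the study will be declared negative and terminated".
- Otherwise the trial goes on with 9 more, which brings the evaluable total to 21.
- Success needs a total of 3 or more responders.

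The null rate is 5% and the target 20%, with "the probabilities of type I and type II error set at 0.1 and 0.2 respectively". No section names an interval or estimator that takes the two stages into account.

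**The concern.** The interval is called exact, and for a single fixed sample it would be. Here the trial ends at 12 patients when none of them responds. Every sequence that begins with 12 non-responders is therefore removed from the possible totals out of 21, and the binomial distribution on 21 no longer describes the data. The tail probabilities that define the interval are then wrong, most of all at the lowest totals.

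Those totals are realistic. At a true 5%, the chance of finishing at 1/21 or 2/21 is 21.5% + 16.4% = 37.9%. In such negative results the upper limit tells the reader how much activity has not been ruled out, so a limit that is too low makes the treatment look more firmly excluded than it is.

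**Working it through.** **Inputs (section 17.1).** Stage 1 has 12 patients and stops at 0 responses. Stage 2 adds 9, for a total of 21. Success is 3 or more responses. The rates are 5% (null) and 20% (target).

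**Two-stage distribution.** Write p for the true rate.

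- P(stop at 0/12) = (1 − p)^12.
- P(stage 2 reached, total s) = c_s · p^s · (1 − p)^(21 − s), where c_s sums C(12, x)·C(9, s − x) over x ≥ 1. This equals C(21, s) − C(9, s).
- c_1 = 21 − 9 = 12; c_2 = 210 − 36 = 174; c_3 = 1330 − 84 = 1246. A plain binomial would use 21, 210 and 1330.

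**The plan's own figures.**

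- Stopping probability at 5%: 0.95^12 = 0.5404 (plan: 54%).
- Type I error: 1 − 0.5404 − 0.2151 − 0.1641 = 0.0804 (limit 0.10).
- Power at 20%: 1 − 0.0687 − 0.0277 − 0.1003 = 0.8033 (plan: at least 80%).

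A search over designs returns 0/12, 2/21 as the minimax design. The design reproduces.

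**Intervals.** The planned interval is Clopper-Pearson on 0/12 or s/21. The two-stage interval orders outcomes as 0/12, 1/21, 2/21 and so on, and solves the two-stage tail probabilities at 0.025.

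| Result | Planned 95% interval | Two-stage 95% interval | Change in upper limit (points) |
|---|---|---|---|
| 0/12 | 0 to 26.5% | 0 to 26.5% | 0 |
| 1/21 | 0.1 to 23.8% | 0.2 to 27.8% | 4.0 |
| 2/21 | 1.2 to 30.4% | 1.3 to 31.6% | 1.3 |
| 3/21 | 3.0 to 36.3% | 3.1 to 36.7% | 0.4 |
| 4/21 | 5.4 to 41.9% | 5.5 to 42.0% | 0.1 |

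Changes are taken from unrounded limits. From 5/21 upward the two intervals agree to 0.2 points or better.

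**Upper-tail error of the planned interval.** This is the chance that the upper limit falls below the true rate.

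- True rate below 23.8%: no result has an upper limit that low, so the error is zero.
- 23.8% to 26.5%: only 1/21 misses, with probability at most 1.2%.
- Just above 26.5%: both 0/12 and 1/21 miss. At p = 0.265, 0.0249 + 0.0067 = 0.0316.
- Just above 30.4%: 0/12, 1/21 and 2/21 miss, 0.0130 + 0.0026 + 0.0165 = 0.0321, the maximum.

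The error exceeds 2.5% only for true rates of about 26.5 to 27.8%, 30.4 to 31.6%, 36.3 to 36.7% and near 42%. The two-stage interval keeps it at or below 2.5%. Two-sided coverage of the planned interval is at least 95.3% for true rates from 0.1% to 70%.

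**Point estimate.** The expected simple proportion is 12p/21 + (9p/21)(1 − (1 − p)^12). At 5% this is 3.84%, a bias of −1.16 points over all trials; at 20% the bias is −0.59. Among trials that reach stage 2 at a true 5%, the average is 0.0384/0.4596 = 8.4%, or +3.4 points. The uniformly minimum-variance unbiased estimate (UMVUE) scores 0 at 0/12, so among the same trials it averages 0.05/0.4596 = 10.9%, or +5.9 points.

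**The case against.** The strongest reply is that nothing the plan promises is broken. It promises 95% coverage and delivers at least 95.3%. For every true rate up to the 20% target the planned upper limit never falls below the truth. The excess tail error appears only at rates above the target, where 1/21 is rare (0.6% at a true 27%). The results that change most, 1/21 and 2/21, are already declared negative. The reversed limits at 0/12 and 1/21 partly reflect 12 patients against 21. All of this stands, and it is why the point is minor. What remains is that the label exact is wrong for this sampling plan, that the 2.5% upper-tail guarantee fails in places, and that a valid interval costs almost nothing.

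A reader might also infer that the reported response rate will be biased low and that the UMVUE should replace it. The documents do not support that. No point estimator is named, so the simple proportion is only the natural reading. The low bias exists only when trials stopped at 0/12 are averaged in. Once stage 2 is reached the simple proportion runs high, and the UMVUE runs higher. At 1/21 the UMVUE is 1/12 = 8.3%, so the nine stage-2 patients do not lower it at all. Its root mean squared error over the whole design is larger at a true 5% (5.8 against 5.1 points), about equal at 10% (7.5), and slightly smaller at 15% (8.5 against 8.9). The choice is a trade-off, not a correction.

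**Conclusion.** The concern holds for the interval and is minor. The binomial interval is not exact for a design that stops at 0/12. Its upper limit is too low by 4.0 points at 1/21, 1.3 at 2/21 and 0.4 at 3/21, and the difference is negligible beyond that. It would be wrong to conclude that the interval falls short of 95% coverage, or that the success rule, type I error or power is affected; none of these is so.

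The figures assume exactly 12 and 21 analysed patients and the ordering 0/12, then totals 1 to 21. The plan allows up to 23 enrolled, and section 17.3 bases the main analysis on eligible patients rather than on the 21 evaluable, so the attained sizes may differ and the limits would shift with them.

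**What to change.** In section 17.1 and the synopsis, state that the 95% interval for the response rate is computed from the two-stage sampling distribution, with outcomes ordered 0/12 and then totals 1 to n, using the actual stage sizes. Name the simple proportion as the reported point estimate. The UMVUE may be shown beside it as an option, described as unbiased only over the whole design, including trials that stop at 0/12.

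The cost is a sentence or two in each place and a few lines of code; patients, data and decision rule stay the same. The downside is a less familiar interval that is slightly wider at low counts. Fixing the method before results are known avoids a later choice between intervals.
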